6.3.4 Duration of Response

Duration of overall response: The duration of overall response is measured from the time measurement criteria are met for CR or PR (whichever is first recorded) until the first date that recurrent or progressive disease is objectively documented.

Duration of stable disease: Stable disease is measured from the start of the treatment until the criteria for progression are met.

6.3.5 Progression-Free Survival (PFS)

PFS is defined as the duration of time from start of treatment to time of progression or death, whichever occurs first

7 NIH REPORTING REQUIREMENTS / DATA AND SAFETY MONITORING PLAN

7.1 DEFINITIONS

Please refer to definitions provided in Policy 801: Reporting Research Events found at:
<https://irbo.nih.gov/confluence/pages/viewpage.action?pageId=36241835#Policies&Guidance-800Series-ComplianceandResearchEventReportingRequirements>.

7.2 OHSRP OFFICE OF COMPLIANCE AND TRAINING / IRB REPORTING

7.2.1 Expedited Reporting

Please refer to the reporting requirements in Policy 801: Reporting Research Events and Policy 802 Non-Compliance Human Subjects Research found at:

<https://irbo.nih.gov/confluence/pages/viewpage.action?pageId=36241835#Policies&Guidance-800Series-ComplianceandResearchEventReportingRequirements>.

Note: Only IND Safety Reports that meet the definition of an unanticipated problem will need to be reported per these policies.

7.2.2 IRB Requirements for PI Reporting at Continuing Review

Please refer to the reporting requirements in Policy 801: Reporting Research Events found at:
<https://irbo.nih.gov/confluence/pages/viewpage.action?pageId=36241835#Policies&Guidance-800Series-ComplianceandResearchEventReportingRequirements>.

7.3 NCI CLINICAL DIRECTOR REPORTING

Problems expeditiously reported to the OHSRP in the NIH eIRB system will also be reported to the NCI Clinical Director/designee; therefore, a separate submission for these reports is not necessary.

In addition to those reports, all deaths that occur within 30 days after receiving a research intervention should be reported via email unless they are due to progressive disease.

To report these deaths, please send an email describing the circumstances of the death to [REDACTED]

7.4 INSTITUTIONAL BIOSAFETY COMMITTEE (IBC) REPORTING CRITERIA

7.4.1 Serious Adverse Event Reports to IBC

The Principal Investigator (or delegate) will notify IBC of any unexpected fatal or life-threatening experience associated with the use of CV301 vaccines as soon as possible but in no

event later than 7 calendar days of initial receipt of the information. Serious adverse events that are unexpected and associated with the use of the CV301 vaccines, but are not fatal or life-threatening, must be reported to the NIH IBC as soon as possible, but not later than 15 calendar days after the investigator's initial receipt of the information. Adverse events may be reported by using the FDA Form 3500a.

7.4.2 Annual Reports to IBC

Within 60 days after the one-year anniversary of the date on which the IBC approved the initial protocol, and after each subsequent anniversary until the trial is completed, the Principal Investigator (or delegate) shall submit the information described below. Alternatively, the IRB continuing review report can be sent to the IBC in lieu of a separate report. Please include the IBC protocol number on the report.

7.4.3 Clinical Trial Information

A brief summary of the status of the trial in progress or completed during the previous year. The summary is required to include the following information:

- the title and purpose of the trial
- clinical site
- the Principal Investigator
- clinical protocol identifiers;
- participant population (such as disease indication and general age group, e.g., adult or pediatric);
- the total number of participants planned for inclusion in the trial; the number entered into the trial to date whose participation in the trial was completed; and the number who dropped out of the trial with a brief description of the reasons
- the status of the trial, e.g., open to accrual of subjects, closed but data collection ongoing, or fully completed,
- if the trial has been completed, a brief description of any study results.

7.4.4 Progress Report and Data Analysis

Information obtained during the previous year's clinical and non-clinical investigations, including:

- a narrative or tabular summary showing the most frequent and most serious adverse experiences by body system
- a summary of all serious adverse events submitted during the past year
- a summary of serious adverse events that were expected or considered to have causes not associated with the use of the gene transfer product such as disease progression or concurrent medications
- if any deaths have occurred, the number of participants who died during participation in the investigation and causes of death

a brief description of any information obtained that is pertinent to an understanding of the gene transfer product's actions, including, for example, information about dose-response, information from controlled trials, and information about bioavailability.

7.5 NIH REQUIRED DATA AND SAFETY MONITORING PLAN

7.5.1 Principal Investigator/Research Team

The clinical research team will meet on a weekly basis when participants are being actively treated on the trial to discuss each participant. Decisions about dose level enrollment and dose escalation will be made based on the toxicity data from prior participants. Evaluation of DLTs (eDLTs; Schema 1 and 2) will occur after all participants are enrolled on a given dose level.

All data will be collected in a timely manner and reviewed by the principal investigator or a lead associate investigator. Events meeting requirements for expedited reporting as described in section **7.2.1** will be submitted within the appropriate timelines.

The principal investigator will review adverse event and response data on each participant to ensure safety and data accuracy. The principal investigator will personally conduct or supervise the investigation and provide appropriate delegation of responsibilities to other members of the research staff.

7.5.2 Data Safety Monitoring Board (DSMB)

The DSMB is an independent group of at least 3 experts that monitors participant safety and advises The Sponsor. DSMB members will be separate and independent of study staff participating in this trial and should not have scientific, financial, or other conflicts of interest related to this trial. The DSMB will consist of members with appropriate expertise to contribute to the interpretation of data from this trial. A quorum will consist of a simple majority.

The DSMB will review cumulative safety data from this trial at least annually.

The DSMB will meet when trial halting criteria (see Section **3.2**) are met, or as requested by the sponsor or PI.

The DSMB will have a final review meeting at the end of the study.

Procedures for DSMB reviews/meetings will be defined in the DSMB charter. The DSMB will review applicable data, including, but not limited to, enrollment, demographics, dosing data, clinical laboratory data, and safety data, at scheduled timepoints during this trial as defined in the DSMB charter. The DSMB will review blinded aggregate data in the open session of the DSMB meetings.

Additional data may be requested by the DSMB, and interim statistical reports may be generated as deemed necessary and appropriate by the Sponsor. As an outcome of each review/meeting, the DSMB will make a recommendation as to the advisability of proceeding with study product administration, and to continue, modify, or terminate this trial.

8 SPONSOR PROTOCOL/SAFETY REPORTING

8.1 DEFINITIONS

8.1.1 Adverse Event

Any untoward medical occurrence in a participant or clinical investigation subject administered a pharmaceutical product and which does not necessarily have a causal relationship with this treatment. An adverse event (AE) can therefore be any unfavorable and unintended sign

(including an abnormal laboratory finding), symptom, or disease temporally associated with the use of a medicinal (investigational) product, whether or not related to the medicinal (investigational) product (ICH E6 (R2))

8.1.2 Serious Adverse Event (SAE)

An adverse event or suspected adverse reaction is considered serious if in the view of the investigator or the sponsor, it results in any of the following:

- Death,
- A life-threatening adverse event (see section [8.1.3](#))
- Inpatient hospitalization or prolongation of existing hospitalization:
 - A hospitalization/admission that is pre-planned (i.e., elective or scheduled surgery arranged prior to the start of the study), a planned hospitalization for pre-existing condition, or a procedure required by the protocol, without a serious deterioration in health, is not considered a serious adverse event.
 - A hospitalization/admission that is solely driven by non-medical reasons (e.g., hospitalization for participant convenience) is not considered a serious adverse event.
 - Emergency room visits or stays in observation units that do not result in admission to the hospital would not be considered a serious adverse event. The reason for seeking medical care should be evaluated for meeting one of the other serious criteria
- Persistent or significant incapacity or substantial disruption of the ability to conduct normal life functions
- A congenital anomaly/birth defect.
- Important medical events that may not result in death, be life-threatening, or require hospitalization may be considered a serious adverse drug experience when, based upon appropriate medical judgment, they may jeopardize the patient or subject and may require medical or surgical intervention to prevent one of the outcomes listed in this definition.

8.1.3 Life-threatening

An adverse event or suspected adverse reaction is considered "life-threatening" if, in the view of either the investigator or sponsor, its occurrence places the patient or subject at immediate risk of death. It does not include an adverse event or suspected adverse reaction that, had it occurred in a more severe form, might have caused death. (21CFR312.32)

8.1.4 Severity

The severity of each Adverse Event will be assessed utilizing the CTCAE version 5.0.

8.1.5 Relationship to Study Product

All AEs will have their relationship to study product assessed using the terms: related or not related.

- Related – There is a reasonable possibility that the study product caused the adverse event. Reasonable possibility means that there is evidence to suggest a causal relationship between the study product and the adverse event.

- Not Related – There is not a reasonable possibility that the administration of the study product caused the event.

8.1.6 Adverse Events of Special Interest (AESI)

An adverse event of special interest (AESI) is one of scientific and medical interest specific to understanding of the Investigational Product(s) and may require close monitoring and rapid communication by the investigator to the sponsor. An AESI may be serious or non-serious. The rapid reporting of AESIs assessed as severe allows ongoing surveillance of these events to characterize and understand them in association with the use of these investigational products. Only AESIs that match the definition of SAE will be reported within 7 days from the knowledge of event. Other non-SAE AESIs do not need to be reported to OSRO but only collected in the clinical database.

The adverse events related to mucosal bleeding, regardless of site, will be collected as an AESI to enable evaluation of potential risk factors, such as site/past radiation/associated infection at site/recent instrumentation and other variables such as time to onset, exposure history, grade of bleeding, anatomical sites, etc. can be collected.

8.2 ASSESSMENT OF SAFETY EVENTS

AE information collected will include event description, date of onset, assessment of severity and relationship to study product and alternate etiology (if not related to study product), date of resolution of the event, seriousness and outcome. The assessment of severity and relationship to the study product will be done only by those with the training and authority to make a diagnosis and listed on the Form FDA 1572 as the site principal investigator or sub-investigator. AEs occurring during the collection and reporting period will be documented appropriately regardless of relationship. AEs will be followed through resolution.

SAEs will be:

- Assessed for severity and relationship to study product and alternate etiology (if not related to study product) by a licensed study physician listed on the Form FDA 1572 as the site principal investigator or sub-investigator.
- Recorded on the appropriate SAE report form, the medical record and captured in the clinical database.
- Followed through resolution by a licensed study physician listed on the Form FDA 1572 as the site principal investigator or sub-investigator.

For timeframe of recording adverse events, please refer to section [6.1](#). All serious adverse events recorded from the time of first investigational product administration must be reported to the Sponsor with the exception of any listed in section [8.4](#).

8.3 REPORTING OF SERIOUS ADVERSE EVENTS

Any AE that meets a protocol-defined serious criteria or meets the definition of Adverse Event of Special Interest that require expedited reporting must be submitted immediately (within 24 hours of awareness) to OSRO Safety using the CCR SAE report form. Any exceptions to the expedited reporting requirements are found in section [8.4](#)

All SAE reporting must include the elements described in [8.2](#).

Following the assessment of the SAE by OSRO, other supporting documentation of the event may be requested by the OSRO Safety and should be provided as soon as possible.

8.4 WAIVER OF EXPEDITED REPORTING TO CCR

As death due to disease progression is part of the study objectives (PFS), and captured as an endpoint in this study, death due to disease progression will not be reported in expedited manner to the sponsor. However, if there is evidence suggesting a causal relationship between the study drug and the event, report the event in an expedited manner according to section **8.3**.

Hospitalization that is deemed to be due to disease progression, and not attributable to the intervention will not be reported as an SAE. The event, and the assessment that it was caused by disease progression will be documented in the medical records. The causality assessment of hospitalization will be re-evaluated any time when new information is received. If the causality assessment changes from disease progression to related to the study intervention, SAE report will be sent to the Sponsor in an expedited manner according to section 8.3. If there is any uncertainty whether the intervention is a contributing factor to the event, the event should be reported as AE or SAE as appropriate.

8.5 SAFETY REPORTING CRITERIA TO THE PHARMACEUTICAL COLLABORATORS

Reporting will be per the collaborative agreement.

8.6 REPORTING PREGNANCY

8.6.1 Maternal exposure

If a participant becomes pregnant during the course of the study, the study treatment should be discontinued immediately, and the pregnancy reported to the Sponsor no later than 24 hours of when the Investigator becomes aware of it. The Investigator should notify the Sponsor no later than 24 hours of when the outcome of the Pregnancy become known.

Pregnancy itself is not regarded as an SAE. However, congenital abnormalities or birth defects and spontaneous miscarriages that meet serious criteria (section 8.1.2) should be reported as SAEs.

The outcome of all pregnancies should be followed up and documented.

8.6.2 Paternal exposure

Male participants should refrain from fathering a child or donating sperm during the study treatment and for 6 months after the last dose of study drug (s).

Pregnancy of the participant's partner is not considered to be an AE. However, the outcome of all pregnancies occurring from the date of the first dose until 6 months after the last dose should, if possible, be followed up and documented. Pregnant partners may be offered the opportunity to participate in an institutional pregnancy registry protocol (e.g., the NIH IRP pregnancy registry study) to provide data about the outcome of the pregnancy for safety reporting purposes.

8.7 REGULATORY REPORTING FOR STUDIES CONDUCTED UNDER CCR-SPONSORED IND

Following notification from the investigator, CCR, the IND sponsor, will report any suspected adverse reaction that is both serious and unexpected. CCR will report an AE as a suspected adverse reaction only if there is evidence to suggest a causal relationship between the study product and the adverse event. CCR will notify FDA and all participating investigators (i.e., all investigators to whom the sponsor is providing drug under its INDs or under any investigator's IND) in an IND safety report of potential serious risks from clinical trials or any other source, as soon as possible, in accordance to 21 CFR Part 312.32.

All serious events will be reported to the FDA at least annually in a summary format.

8.8 SPONSOR PROTOCOL DEVIATION REPORTING

A Protocol Deviation is defined as any non-compliance with the clinical trial Protocol, Manual of Operational Procedures (MOP) and other Sponsor approved study related documents, GCP, or protocol-specific procedural requirements on the part of the participant, the Investigator, or the study site staff inclusive of site personnel performing procedures or providing services in support of the clinical trial.

It is the responsibility of the study Staff to document any protocol deviation identified by the Staff or the site Monitor in the CCR Protocol Deviation Tracking System (PDTs) online application. The entries into the PDTs online application should be timely, complete, and maintained per CCR PDTs user requirements.

In addition, any deviation to the protocol should be documented in the participant's source records and reported to the reviewing IRB per their guidelines. OSRO required protocol deviation reporting is consistent with E6(R2) GCP: Integrated Addendum to ICH E6(R1): 4.5 Compliance with Protocol; 5.18.3 (a), and 5.20 Noncompliance; and ICH E3 16.2.2 Protocol deviations.

9 CLINICAL MONITORING

Clinical site monitoring is conducted to ensure:

- that the rights of the participants are protected;
- that the study is implemented per the approved protocol, Good Clinical Practice and standard operating procedures; and
- the quality and integrity of study data and data collection methods are maintained.

Monitoring for this study will be performed by NCI CCR Office of Sponsor and Regulatory Oversight (OSRO) Sponsor and Regulatory Oversight Support (SROS) Services contractor. Clinical site monitoring activities will be based on OSRO standards, FDA Guidance E6(R2) Good Clinical Practice: Integrated Addendum to ICH E6(R1) March 2018, and applicable regulatory requirements.

Details of clinical site monitoring will be documented in a Clinical Monitoring Plan (CMP) developed by OSRO. CMPs will be protocol-specific, risk-based and tailored to address human subject protections and integrity of the study data. OSRO will determine the intensity and frequency of monitoring based on several factors, including study type, phase, risk, complexity, expected enrollment rate, and any unique attributes of the study and the site. The Sponsor will conduct a periodic review of the CMP to confirm the plan's continued appropriateness. A change to the protocol, significant or pervasive non-compliance with GCP, or the protocol may trigger CMP updates.

OSRO SROS Monitoring visits and related activities will be conducted throughout the life cycle of each protocol. The first activity is before the study starts to conduct a Site Assessment Visit (SAV) (as warranted), followed by a Site Initiation Visit (SIV), Interim Monitoring Visit(s) (IMVs), and a study Close-Out Visit (COV).

Some monitoring activities may be performed remotely, while others will occur at the study site(s). Monitoring visit reports will describe visit activities, observations, and associated action items or follow-up required for resolution of any issues, discrepancies, or deviations. Monitoring reports will be distributed to the study PI, NCI CCR QA, CCR Protocol Support Office, coordinating center (if applicable), and the Sponsor regulatory file.

The site Monitor will inform the study team of any deviations observed during monitoring visits. If unresolved, the Monitor will request that the site Staff enter the deviations in the CCR Protocol Deviation Tracking System (PDTs) for deviation reporting to the Sponsor and as applicable per institutional and IRB guidance.

10 STATISTICAL CONSIDERATIONS

10.1 STATISTICAL HYPOTHESIS

Primary Objectives:

- Arm 1 (Sequential Dose Escalation):
 - To evaluate the safety and tolerability of single agent SX-682.
 - To determine the MTD of SX-682 followed by M7824 and CV301 in participants with advanced or metastatic solid tumors. If the MTD is not reached the study will be focused to describe the safety and tolerability of SX-682 followed by M7824 and CV301.
- Arm 2 (Combination Dose Escalation):
 - To determine the RP2D of SX-682 with M7824 and CV301 in participants with advanced or metastatic solid tumors. If the MTD is not reached the study will be focused to describe the safety and tolerability of the drug combination.
- Arm 3 (Expansion):
 - To evaluate preliminary efficacy based on Objective Response Rate (ORR), in each disease cohort separately.

Secondary Objectives:

- Arms 1 and 2 (Dose Escalations):
 - To characterize the PK/PD profile of SX-682 as a single agent and in combination.
- All Arms:
 - To evaluate preliminary efficacy: Disease control rate (DCR) and Progression-free survival (PFS) using RECIST1.1

10.2 SAMPLE SIZE DETERMINATION

The trial will begin with two phase I evaluations (Cohort 1, Arms 1 and 2; Dose Escalation) as follows: initially participants will be enrolled in Arm 1 involving monotherapy with SX-682 followed by M7824 + CV301. This will initially include up to 3 dose levels, with 3 participants per dose level if no DLTs are experienced. However, if in any of the dose levels, a DLT is identified in the 3 participants, 3 more participants will be enrolled in that dose level, with subsequent escalation only if there are ≤ 1 DLTs in 6 participants. Thus, up to 18 participants may be enrolled in these first 3 dose levels. If there is one or more DLTs identified in the first 3 dose levels, escalation will continue to DL4 and 5 using the above 3+3 design. If there are no DLTs in the first 3 dose levels, then participants will be enrolled to Arm 2. As a result, depending on toxicities identified, between 9 and 30 participants may be treated within this sequential dose escalation arm.

In Arm 2, a combination arm with SX-682 followed by the triplet combination (SX-682, M7824, CV301), up to 5 dose levels may be explored. Using a standard 3+3 design, up to $5 \times 6 = 30$ participants may be included in this arm. Thus, up to $30 + 30 = 60$ total participants may be treated in the phase I portion (Cohort 1, Arms 1 and 2) of the trial.

The phase II evaluation (Arm 3) will take place separately in two cohorts:

TNBC:

Based on prior studies [70-72], the clinical response rate for similar participants with advanced disease receiving a single agent checkpoint inhibitor is expected to be 8-10%. Thus, an observed response rate of approximately 15% or higher would be desirable.

In Arm 3, Cohort 2 (TNBC), the trial will be conducted using a Simon minimax two-stage phase II trial design [99] to rule out an unacceptably low response rate (CR+PR) of 5% ($p_0=0.05$) in favor of an improved response rate of 20% ($p_1=0.20$). With $\alpha=0.10$ (probability of accepting a poor treatment=0.10) and $\beta = 0.20$ (probability of rejecting a good treatment=0.20), the first stage will enroll 12 evaluable participants, and if 0 of the 12 has a response, then no further participants will be accrued in that cohort. If 1 or more of the first 12 participants has a response, then accrual would continue until a total of 21 evaluable participants have been treated in that cohort. As it may take up to several months to determine if a participant has experienced a response, a temporary pause in the accrual may be necessary to ensure that enrollment to the second stage is warranted. If there are 1-2 participants with a response out of 21 participants in this cohort, this would be an uninterestingly low response rate. If there were 3 or more of 21 (14.3%) who experienced a response, this would be sufficiently interesting to warrant further study in later trials. Under the null hypothesis (5% response rate), the probability of early termination is 54.0%.

HPV negative HNSCC:

Based on prior studies [82, 87, 88], the clinical response rate for similar participants with this disease is expected to be 13-18%. Thus, an observed response rate of greater than 25% would be desirable.

In Arm 3, Cohort 3 (HPV negative HNSCC), the trial will be conducted using a Simon minimax two-stage phase II trial design[99] to rule out an unacceptably low response rate (CR+PR) of 15% ($p_0=0.15$) in favor of an improved response rate of 40% ($p_1=0.40$). With $\alpha=0.10$ (probability of accepting a poor treatment=0.10) and $\beta = 0.20$ (probability of rejecting a good treatment=0.20), the first stage will enroll 9 evaluable participants, and if 0 to 1 of the 9 have a response, then no further participants will be accrued in that cohort. If 2 or more of the first 9 participants have a response, then accrual would continue until a total of 16 evaluable participants have been treated in that cohort. As it may take up to several months to determine if a participant has experienced a response, a temporary pause in the accrual may be necessary to ensure that enrollment to the second stage is warranted. If there are 2-4 participants with a response out of 16 participants in this cohort, this would be an uninterestingly low response rate. If there were 5 or more of 16 (31.3%) who experienced a response, this would be sufficiently interesting to warrant further study in later trials. Under the null hypothesis (15% response rate), the probability of early termination is 60.0%.

It is expected that up to 1.5 years may be required to enroll up to 60 participants in Arms 1 and 2. It is then expected that 2-3 years may be required to complete accrual to Arm 3. Thus, accrual is expected to be completed in 4-5 years. The total number of evaluable participants is no more than $60+21+16=97$. To allow for a small number of inevaluable participants, the accrual ceiling for treated participants in the dose escalation and expansion cohorts combined will be set at 105 participants

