3.1.3 Sequential Dose Escalation (Arm 1)

In Arm 1 participants will receive SX-682 as monotherapy for 2 weeks during the lead-in (Days -14L to -1L) and then continue treatment with M7824 and CV301 starting Cycle 1, Day 1.

The dose escalation will start from dose level 1 and continue until dose level 3 (**Table 4**) in sequential order using a standard 3+3 design (**Table 5**). Aside from looking at DLTs within a given dose level, the total number of DLTs will also be evaluated among the initial 3DLs in Arm 1 to guide further safety assessments. If there are 0 DLTs reported in the initial 3 DLs (minimum of 12 participants) in Arm 1, then Arm 2 can open as depicted in Schema 2 with starting at DL2. If there is 1 or more DLTs identified among all the participants in the first 3 DLs, enrollment in Arm 1 will continue with the next participants being enrolled on DL4 then DL5, using a 3+3 design in order to determine the maximally tolerated dose (MTD) before proceeding to Arm 2, DL 1.

Dose escalation will proceed in groups of 3–6 participants. The MTD is the dose level at which no more than 1 of up to 6 participants experience DLT during 28 days of treatment, and the dose below that at which at least 2 (of ≤ 6) participants have DLT as a result of the drug.

Table 4: Dose levels of SX-682

Dose Escalation Schedule		
Dose Level	Dose of SX-682	Total SX-682 daily dose
Level 1	25 mg by mouth twice daily	50 mg
Level 2	50 mg by mouth twice daily	100 mg
Level 3	100 mg by mouth twice daily	200 mg
Level 4	200 mg by mouth twice daily	400 mg
Level 5	400 mg by mouth twice daily	800 mg

SX-682 is dispensed as a 25mg tablet. M7824 and CV301 will be given at fixed doses.

Table 5. Escalation Decision Rules

Number of Participants with DLT at a Given Dose Level	Escalation Decision Rule*
0 out of 3	Enter up to 3 participants at the next dose level
≥ 2	Dose escalation will be stopped. This dose level will be declared the maximally administered dose (highest dose administered). Up to three (3) additional participants will be entered at the next lowest dose level if only 3 participants were treated previously at that dose.

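### Section 10.2 lets Arm 1 hand over to Arm 2 after 9 DLT-free participants, while Sections 3.1.3 and 3.1.4 together require 12, with 6 of them at dose level 3.

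*Combined protocol and SAP*

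**What the plan says.** **Section 10.2 (Sample Size Determination).** Arm 1 begins with up to three dose levels, "with 3 participants per dose level if no DLTs are experienced". A level takes three more participants only if a DLT is seen in its first three. The hand-over rule follows: "If there are no DLTs in the first 3 dose levels, then participants will be enrolled to Arm 2". From these rules the section concludes that "between 9 and 30 participants may be treated within this sequential dose escalation arm".

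**Section 3.1.3 (Arm 1).** "The dose escalation will start from dose level 1 and continue until dose level 3". The hand-over rule here carries a count: "If there are 0 DLTs reported in the initial 3 DLs (minimum of 12 participants) in Arm 1, then Arm 2 can open", with Arm 2 starting at dose level 2. If one or more DLTs occur in the first three levels, "enrollment in Arm 1 will continue with the next participants being enrolled on DL4 then DL5", to find the MTD "before proceeding to Arm 2, DL 1".

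**Section 3.1.4 (Arm 2).** Two starting conditions are given. Six participants treated at Arm 1 dose level 3 without a DLT lead to a start at dose level 2. One or more DLTs at Arm 1 dose levels 1 to 3 lead to a start at dose level 1. If the Arm 1 MTD is dose level 1 or 2, an amendment justifying continuation is required.

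**The concern.** The same data, three participants at each of three levels and no DLT, lead to different actions. Section 10.2 moves to Arm 2. Sections 3.1.3 and 3.1.4 are not satisfied until three more participants have been treated at dose level 3.

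The gate decides when the combination arm opens and at which SX-682 level it starts. On one branch it also decides whether the study can continue without an amendment.

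If Section 10.2 is followed, the trial reaches a state that Section 3.1.4 does not cover: there are not six DLT-free participants at dose level 3, and there is no DLT either. Section 8.8 treats any non-compliance with the protocol as a deviation, so after 0 of 9 either course departs from one section.

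**Working it through.** **1. Reproduce the figures in Section 10.2 under its own rules.**
- DLT-free route through three levels: 3 × 3 = 9. This matches the stated lower bound.
- Maximum in the first three levels: 3 × 6 = 18. This matches.
- Maximum over five levels: 5 × 6 = 30. This matches.

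The 9 is therefore the result of an enrolment rule plus a hand-over rule. It is the minimum of the DLT-free route only; a stop for toxicity at dose level 1 or 2 could treat fewer.

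**2. Count the same route under Section 3.**
- Dose levels 1 and 2: three each, since Section 3.1.2 opens the next level after no DLT in three.
- Dose level 3: six, from Section 3.1.4.
- Total: 3 + 3 + 6 = 12. This is the count in Section 3.1.3, so Sections 3.1.3 and 3.1.4 agree with each other and differ from Section 10.2 by 12 − 9 = 3.

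**3. What the three further participants at dose level 3 can do.** Reading Section 3.1.3 together with its 3+3 rules in Table 5:
- No DLT: Arm 2 opens at dose level 2.
- Exactly one DLT (1 of 6): Arm 1 continues to dose levels 4 and 5, and Arm 2 later starts at dose level 1.
- Two or more: dose level 3 becomes the maximally administered dose. The MTD can then be no higher than dose level 2, and an MTD of dose level 1 or 2 triggers the amendment requirement in Section 3.1.4.

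**4. How often the route changes.** The available text gives no DLT rate, so the dose level 3 rate *p* is assumed to be 10%, 20% or 33%. Given 0 of 3 at dose level 3, for the next three participants:

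| Outcome | Formula | p = 0.10 | p = 0.20 | p = 0.33 |
|---|---|---|---|---|
| Any DLT (route changes) | 1 − (1 − p)³ | 0.271 | 0.488 | 0.699 |
| Exactly one | 3p(1 − p)² | 0.243 | 0.384 | 0.444 |
| Two or more | 3p²(1 − p) + p³ | 0.028 | 0.104 | 0.255 |

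**5. The same question before any data.** With a common DLT rate *r* at dose levels 1 and 2, the chance of reaching 0 of 9 and then having the two gates take different routes is (1 − r)⁶ × (1 − p)³ × [1 − (1 − p)³]:

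| r | p = 0.10 | p = 0.20 | p = 0.33 |
|---|---|---|---|
| 0 | 0.198 | 0.250 | 0.210 |
| 0.05 | 0.145 | 0.184 | 0.155 |
| 0.10 | 0.105 | 0.133 | 0.112 |

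For example, with r = 0 and p = 0.20: 1 × 0.512 × 0.488 = 0.250.

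**6. Evidence at dose level 3 under each gate.** The one-sided 95% upper bound on the DLT rate after no events in n participants is 1 − 0.05^(1/n). This is 63.2% for n = 3 and 39.3% for n = 6.

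**The case against.** The strongest reply is that Section 10.2 is a planning section. Its hand-over sentence gives no number, the range of 9 to 30 contains 12, and the operational sections agree with each other, so a site working from Section 3 has a usable count. On that reading the 9 merely omits three participants. This does not remove the conflict: Section 10.2 sets out how many to enrol per level without DLTs and when to move on, and presents its range as the consequence. No available text gives Section 3 precedence.

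Some narrower points stand:
- The count of 12 appears only in Section 3.1.3 and the six at dose level 3 only in Section 3.1.4. Joining them as 3 + 3 + 6 is an inference, though the two figures fit exactly.
- Section 10.2 names no Arm 2 starting level. The gap in Section 3.1.4 after 0 of 9 is a consequence of the same mismatch, not a second defect.
- The branch for two or more DLTs reads Section 3.1.3 through Table 5. Taken alone, the Section 3.1.3 sentence on one or more DLTs continues to dose level 4. Its reference to a 3+3 design, and the limit of one DLT in six in Section 10.2, support the Table 5 reading.
- Section 3.1.2 and Table 5 do not themselves tell a site to enrol participants four to six at dose level 3 after 0 of 3, so they belong in the reconciliation.
- The probabilities rest on assumed rates. They show how much the choice could matter and do not forecast this trial.
- Schemas 1 and 2 are not reproduced and may show a gate. A figure that did so would still leave the conflicting sentences in place.

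**Conclusion.** The concern holds. On the DLT-free route the plan gives two gates for moving from Arm 1 to Arm 2: 9 participants in Section 10.2 and 12 under Sections 3.1.3 and 3.1.4 together. The certain effect is three participants at dose level 3 and a lower bound that does not match the operational sections.

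The possible effect is a different escalation route. Given 0 of 3 at dose level 3, the chance is 27% to 70% over assumed rates of 10% to 33% there. Before any data it is about 10% to 25%, with assumed rates of 0% to 10% at dose levels 1 and 2. These figures assume independent participants and a constant rate within each level.

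The maxima are unaffected: 30 in Arm 1, 60 in phase I, 97 evaluable, and a ceiling of 105. This should be corrected, but it does not undermine the sample size.

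**What to change.** State one DLT-free gate for the move from Arm 1 to Arm 2, identically in Sections 10.2, 3.1.3 and 3.1.4, and check Section 3.1.2, Table 5 and Schemas 1 and 2 against it. Restate the Arm 1 lower bound in Section 10.2 to match (9 or 12), and label it as the minimum of the DLT-free route. Word the starting-level conditions in Section 3.1.4 so that every state from which Arm 2 can open is covered.

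Which count and which starting level apply is for the sponsor to decide; no view is taken here. The cost is protocol wording only, with no change to the maxima or the accrual ceiling.
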